# **STUDY DESIGN AND METHODS**

2

This will be a prospective randomized study to compare auricular battlefield acupuncture to sham auricular battlefield acupuncture in patients undergoing general surgery and urology cases with general anesthesia. Participants in the study will be randomly assigned to either receive auricular battlefield acupuncture (treatment group) or simulated (placebo; control group) auricular battlefield acupuncture. Battlefield acupuncture needles will be utilized in the test arm and blunt needle pressing and covering with acupuncture stickers will be utilized in the control arm as a sham treatment. Location of needles and stickers will be placed according to 5 VA approved BFA auricular acupuncture points associated with PONV, pain, and anxiety respectively (Figure 1; 3). In both arms, the treatment ear will be covered after treatment so as to blind the patient. Both battlefield acupuncture and control groups will receive small band aids on the battlefield acupuncture needle sites. Both the evaluators for post procedure assessment along with the patient will be blinded in regards to what group they are in.

Figure 1. Battlefield acupuncture points.

Source: Teresa M. Kerge et al 2013.US Service Members With Polytrauma. Practical Pain Managementhttp://www.practicalpainmanagement.c om/pain/spine/trauma/us-servicemembers-polytrauma

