#### **Exclusion Criteria:**

- 1 Coagulopathies
- 2 Patients with continuous epidural
- 3 Uncooperative patient
- 4 Psychiatric disorders and language deficiencies that may interfere with the assessment of pain
- 5 Insufficient understanding of the pain scoring system.
- 6 Outpatient stay

This study will be performed at the John D. Dingell VA Medical Center. Only a trained MD anesthesiologist will recruit patient in the preoperative period, where informed consent will be obtained. Computerized randomization will take place at the time the patient presents for surgery. Consent will be taken preoperatively.

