#### **Acupuncture Plan**

Typically acupuncture needles which are semi-permanent needles have the characteristics of remaining in the ear acupoints for up to 3-4 days before being pushed out toward to the surface by the previous flattened epidermis. The test arm (treatment group) will received actual acupuncture needles, while the control arm will received sham or placebo acupuncture via pressing of a blunt needle on the specified BFA locations and then application of adhesive stickers. In the control group simulating acupuncture, the needles will never enter the patients' skin and will give the impression to the patient that the procedure has taken place. The ear

treated will be covered with a bandage via non-skin sensitive tape so as to blind the patient to which treatment group they are in.

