### Data:

Data gathering will be performed by [name], MD and/or a CRNA. Data collection will occur in the PACU (Post-Anesthesia Care Unit) before the PACU nurses evaluate the patient for discharge. Assessment will occur at 1 hour and 24 hour post procedure. The assessment will occur on the next day by either a medical student and/or CRNA at the patients' bed side.

Assessment of the battlefield acupuncture efficacy will be performed by testing the incidence of PONV, incidence of postoperative anxiety, and pain. Pain will be assessed via the visual analog scale (VAS) scoring system.

A study investigator will record the following:

- 1. At times 1 hour and 24 hours the following will be assessed:
- 2. Incidence of PONV
- 3. Incidence of postoperative anxiety
- 4. Pain score on an 11-point (0 to 10) Visual Analog Scale (VAS) at rest and with activity
- 5. Postoperative opioid consumption via morphine equivalents used
- 6. Patient satisfaction with analgesia score (0 to 100%)

7. Any occurrence of acupuncture site infection, acupuncture site bleeding, allergic reaction to acupuncture needles, or scar tissue formation at site of acupuncture needle.

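### Minor: the allergy item names a cause that a blinded evaluator cannot know, and no eligibility criterion answers the allergy risk the protocol lists

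*Combined protocol and SAP*

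**What the plan says.** **Harm item.** In the Data section, item 7 covers infection and bleeding at the site, and then "allergic reaction to acupuncture needles, or scar tissue formation at site of acupuncture needle". It is the only local-harm item. The section Risks and Side Effects-Acupuncture lists allergy in the same way, for needles only.

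**What touches the ear.** Under Study Design and Methods, "Both battlefield acupuncture and control groups will receive small band aids on the battlefield acupuncture needle sites". Under Acupuncture Plan, the sham is "pressing of a blunt needle on the specified BFA locations and then application of adhesive stickers", and "In the control group simulating acupuncture, the needles will never enter the patients' skin". The same section says the ear "treated will be covered with a bandage via non-skin sensitive tape so as to blind the patient".

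**Blinding.** Study Design and Methods states that both the patient and the post-procedure evaluators are blinded to group.

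**Eligibility.** The Exclusion Criteria list six items, from "Coagulopathies" to outpatient stay. None concerns allergy to metal, adhesive or dressing, and nor does any inclusion criterion.

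**The concern.** An item worded by cause can be applied as written only by someone who knows whether the cause was present. Here the evaluator is not meant to know whether there is a needle under the dressing. The form offers no place for a skin reaction whose cause is unknown or suspected to be the adhesive.

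What is at stake is the usefulness of the sham arm for harms. It could supply the background rate of reactions to pressing, stickers, band aids and dressing, but only if every local reaction is counted by the same rule in both arms.

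The eligibility question is separate. The protocol names allergy as a risk of the procedure but does not say what happens when a patient reports a relevant sensitivity beforehand.

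**Working it through.** **1. Exposure at the treated ear, by arm**

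| Exposure | Needle arm | Sham arm | Source |
|---|---|---|---|
| Needle through the skin | Yes | No | Acupuncture Plan |
| Needle contact with the skin surface | Yes | Yes, blunt needle pressed | Acupuncture Plan |
| Adhesive stickers | Not clearly stated | Yes | Study Design; Acupuncture Plan |
| Band aids | Yes | Yes | Study Design |
| Bandage and tape | Yes | Yes | Study Design; Acupuncture Plan |

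Neither needle contact nor adhesive is confined to one arm.

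**2. What the recorded rate estimates.** The symbols are mine and the documents give no values. Suppose each patient has at most one reaction, and let:

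- n = rate of needle-caused reactions in the needle arm, and c = rate of reactions to blunt-needle contact in the sham arm;
- a₁ and a₂ = rates of adhesive-caused reactions in the needle and sham arms;
- s = chance that a needle-caused reaction is ticked under item 7, and q = the same chance for an adhesive-caused reaction.

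A blinded evaluator applies the same s and q in both arms, so:

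- recorded rate, needle arm = s·n + q·a₁
- recorded rate, sham arm = s·c + q·a₂
- difference = s·(n − c) + q·(a₁ − a₂)

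The documents give no rule that fixes s or q, so neither arm's rate can be interpreted. If a₁ = a₂, adhesive reactions cancel from the expected difference, which is then (n − c) shrunk by s. With a cause-neutral item recorded in full, s = q = 1 and the difference is (n − c) + (a₁ − a₂). That is a well-defined contrast of the two procedures as delivered. It isolates the needle only if adhesive exposure is equal and c is negligible.

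**3. Scale.** The documents state no harm rate, so there is no harms figure to reproduce. Their one computed figure, 72 patients (36 per group), is for opioid consumption. Its control rate is not stated, and nothing here depends on it beyond the count of 36.

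- One reaction counted or not counted: 1/36 = 2.8 percentage points. This is true of any event in an arm of 36.
- No events in 36: one-sided 95% upper bound = 1 − 0.05^(1/36) = 8.0%.
- Fisher's exact test, which the Statistical Analysis section names for proportions, at 36 v 36: 5 v 0 gives p = 0.054 and 6 v 0 gives p = 0.025. At least 6 v 0 is needed for p ≤ 0.05.

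Harms will therefore be read descriptively, so the definition of the count matters more than the test.

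**4. Named risks against eligibility.** Bleeding is a listed risk, and the first exclusion (coagulopathies) bears on it. Allergy is on the same list. The other five exclusions concern epidurals, cooperation, psychiatric or language problems, understanding of the pain score, and outpatient stay. The inclusion criteria concern physical status, age and scheduled surgery, consent, and inpatient stay. A patient with a known sensitivity passes all of them.

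**The case against.** A reader might infer more than the documents support, in three ways.

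*That adhesive reactions will be recorded as needle allergy.* No section sets an attribution rule. The documents show only that this can happen, as can non-recording.

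*That reactions will be lost from the sham arm alone, biasing the comparison one way.* A blinded evaluator cannot drop reactions selectively by arm, so the misclassification falls on both arms alike. One-sided distortion would need a failure of blinding, which the documents do not show. Nor is a needle-related event impossible in the sham arm, because the blunt needle touches the skin.

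*That the problem can be sized from an assumed prevalence of metal or adhesive allergy.* That would count patients who carry an allergy. It would not count reactions, still less misclassified ones, and the documents give no figure linking these.

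Other points on the plan's side also stand. The tape is described as non-skin sensitive, although stickers and band aids are not. The Study Design section uses needle sites as a location in both arms, so the scar item can be read as a place. That reading does not rescue the allergy item, which names the needles as the cause. The analysis section plans no specific allergy comparison. Naming a risk does not oblige a matching exclusion, and the consent pages are not available, so how allergy is disclosed to patients cannot be judged.

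**Conclusion.** The concern holds as a minor gap in the definition of one harm and in the handling of one named risk. As worded, the allergy item cannot be applied by the blinded evaluator the protocol specifies, and its per-arm rate is not interpretable. The eligibility text is silent on a risk listed elsewhere in the protocol.

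The number of reactions affected is unknown, because the documents give no rate. The reasoning assumes that blinding works as stated and that the evaluators who complete item 7 are the blinded ones. It also takes the stickers as described, for the sham arm. Opioid use, pain, PONV, anxiety and the sample size are untouched. The change is worth making because it costs almost nothing.

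**What to change.** **Data section, item 7.** Replace the allergy entry with: *any local skin or allergic reaction at the treated ear (point sites or under the dressing)*. Record it in the same way in both arms at both assessments. Note any suspected cause while the evaluator is still blinded. Do not assign cause after unblinding, because knowing the arm would bias the judgement. Compare the arms on all such reactions, and report suspected cause descriptively. Take the other assessments before anyone looks under the dressing, since what is there may reveal the allocation.

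**Eligibility.** Reconcile the Exclusion Criteria with Risks and Side Effects-Acupuncture, and state how a known sensitivity to the study materials is handled at screening. What that rule should be is for the sponsor to decide.

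**Cost.** A form edit, one screening question and possibly a few fewer eligible patients. No change to the sample size or the efficacy analysis.

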#### **Statistical Analysis:**

An unpaired students-t-test procedure (two-sample assuming equal variances, two-tail significance p<0.05, 95% confidence interval) was performed to examine mean differences between the two

study groups on all continuously scaled variables. A Repeated measures ANOVA will be used to measured differences between time for continuous variables at the 2 measured time points (1 hour and 24 hours). Assumptions of normality and/or homogeneity of variance will be checked and verified. Comparisons between study groups on proportional differences will be examined using a non-parametric Fisher's Exact Chi-square test, when applied to 2x2 tables. Statistical significance will be set at a p-value  $\leq 0.05$ . All continuous data will be expressed as the mean with 95% upper and lower confidence intervals or Mean  $\pm$  Standard deviation.

A binary outcome, superiority power analysis based on a rate of 33% reduction of opioid consumption in the auricular battlefield acupuncture group compared to controls (sham auricular battlefield acupuncture) concluded 72 participants (36 patients per group) would be necessary to achieve 80% power with a p<0.05.

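### Preoperative opioid use is neither an exclusion nor a listed data item, so the unadjusted t-test on morphine equivalents may give up precision that one recorded covariate would recover

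*Combined protocol and SAP*

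**What the plan says.** All references are to the combined protocol and SAP.

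- **Eligibility.** The Inclusion Criteria admit ASA classes 1 to 4 and ages 18 to 100. The Exclusion Criteria give six reasons for exclusion. One concerns analgesic technique ("Patients with continuous epidural"), but none concerns opioid use before surgery.
- **Data.** The listed items are postoperative assessments at 1 and 24 hours, plus acupuncture-site complications. The opioid item is "Postoperative opioid consumption via morphine equivalents used". No preoperative opioid item appears.
- **Analysis.** The Statistical Analysis section names "An unpaired students-t-test procedure (two-sample assuming equal variances, two-tail significance p<0.05, 95% confidence interval") and applies it to differences between "study groups on all continuously scaled variables". The other model for continuous data is directed at time: "A Repeated measures ANOVA will be used to measured differences between time for continuous variables at the 2 measured time points". No covariate is named for either. Normality and equal variances are to be checked, but no alternative is given if the check fails.
- **Randomisation.** It is computerised, and no stratification is stated.
- **Sample size.** The basis is "A binary outcome, superiority power analysis based on a rate of 33% reduction of opioid consumption", which "concluded 72 participants (36 patients per group) would be necessary to achieve 80% power with a p<0.05".

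**The concern.** Opioid requirement comes first in the hypothesis, and opioid consumption is the quantity on which the trial is sized, so this is where lost precision costs most. If patients already taking opioids consume more after surgery, a minority of them can supply a large share of the variance in a comparison of 36 against 36. The unadjusted t-test leaves all of that variance in its error term. The two arms may also receive unequal numbers of such patients by chance. If prior use is not collected, a reader of the results can neither check the balance nor adjust for it.

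Whether to exclude prior users is a design trade-off and is not questioned here. Recording the variable and using it does not involve that trade-off.

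**Working it through.** **1. The plan's own figure.** The planned 36 per group cannot be reproduced from the stated inputs, because no control rate is given and the 33% is not said to be absolute or relative. The formula is n = [1.96·√(2p̄q̄) + 0.8416·√(p₁q₁ + p₂q₂)]² / (p₁ − p₂)².
- Absolute drop, 0.66 v 0.33: (1.386 + 0.562)² / 0.1089 = 34.8, so 35 per group.
- Relative drop, 0.88 v 0.59: 36 per group. At a control rate of 0.50 it is 140.

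Either way this is a calculation for proportions. On the t-test scale, 36 per arm gives 80% power at d = (1.96 + 0.8416)·√(2/36) = 0.66. For a 33% lower mean, that requires a coefficient of variation (CV) of 0.33/0.66 = 0.50. The documents give no standard deviation, so the stated 80% does not carry over to the t-test on morphine equivalents.

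**2. Inputs for the effect of adjustment.** From the plan: 36 per arm, two-sided 5%, a 33% reduction (taken here as a ratio of means of 0.67). Assumed, because the documents are silent: proportion of prior users p = 10%, 20% or 30%; consumption multiplier m = 2 or 3; within-group lognormal CV = 0.6 or 0.8.

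**3. Simulation.** Twelve scenarios, 8,000 trials each, comparing the pooled t-test with a linear ANCOVA on treatment and prior use (yes/no). Examples of power:

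| Users | m | CV | t-test | ANCOVA |
|---|---|---|---|---|
| 10% | 2 | 0.6 | 70% | 77% |
| 10% | 2 | 0.8 | 51% | 54% |
| 20% | 2 | 0.6 | 66% | 76% |
| 20% | 3 | 0.6 | 47% | 70% |
| 20% | 3 | 0.8 | 35% | 47% |

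Over all twelve, the gain is about 3–10 points at m = 2 and 8–24 points at m = 3. Repeat runs differ by a point or two. Type I error stays near 5%.

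**4. Check by hand (p = 20%, m = 2, CV = 0.6).** Take the mean in non-users as 1.
- Between-group variance: p(1 − p)(m − 1)² = 0.16.
- Within-group variance: CV²·[(1 − p) + p·m²] = 0.36 × 1.6 = 0.576.
- Share explained by prior use: R² = 0.16/0.736 = 0.22.
- Overall CV: √0.736/1.2 = 0.715. The treated arm's SD is 0.67 times the control SD, so the pooled SD is √((1 + 0.67²)/2) = 0.851 of control, and d = 0.33/(0.715 × 0.851) = 0.542.
- Unadjusted power: Φ(0.542·√18 − 1.96) = Φ(0.34) = 63%.
- Adjusted: d/√(1 − 0.217) = 0.613, and Φ(0.613·√18 − 1.96) = Φ(0.64) = 74%.

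The gain of about 11 points agrees with the simulated 66% v 76%.

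**5. Chance imbalance.** With 20% users and two independent Binomial(36, 0.2) counts, the arms differ by 5 or more users with probability 0.183 (0.075 at 10%, 0.246 at 30%). The shift in the mean, relative to the control mean, is (gap/36)(m − 1)/[1 + p(m − 1)].
- Gap 5, m = 2: 0.139/1.2 = 12%.
- Gap 5, m = 3: 0.278/1.4 = 20%.
- Gap needed for a 33% shift at m = 3: 36 × 0.33 × 1.4/2 = 8.3, so 9 users. The probability of a gap that large in either direction is 1.2%.
- Gap needed at m = 2: 36 × 0.33 × 1.2 = 14.3 users, which is practically impossible.

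**The case against.** The strongest reply is that nothing here is an error. Randomisation makes the unadjusted difference unbiased, the t-test's standard error already allows for chance imbalance, and its type I error stays near 5%. This stands: the point is about precision and about how convincing a single result will be.

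The size of the gain is also not a property of this plan. Prevalence, multiplier and CV are all assumed, and gains above 20 points need threefold consumption, the lower CV and 20–30% users. This stands too, so the range must always carry its assumptions.

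A third reply is that most of the power shortfall in these scenarios comes from skew, which a raw-scale ANCOVA leaves in place. That ANCOVA stays below 80% in all twelve scenarios (47–78%), and an unadjusted t-test on log consumption beats it in nine of them (for example 81% v 78% at 10%, m = 2, CV 0.6). This is a fair criticism of raw-scale adjustment alone. It argues for adding a log-scale model, where adjustment helps as well.

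Finally, the Data list also omits age and ASA class, although both are needed for eligibility. The list therefore shows that prior opioid use is not specified for collection. It does not show that the information would be unavailable from the chart.

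**Conclusion.** The point holds as a cheap improvement in precision. Prior users are eligible, prior use is not a listed item, and the planned comparison ignores it. If prior use predicts consumption, adjustment gains power: about 3–10 points at twofold and 8–24 points at threefold consumption, given 10–30% users, CV 0.6–0.8, a true 33% reduction and 36 per arm.

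Three stronger readings are not supported:
- **That the plan loses a known amount of power.** The documents give no prevalence, no standard deviation and no measure of how well prior use predicts consumption.
- **That imbalance could readily mimic or hide the planned effect.** A 5-user gap, seen in about 18% of trials with 20% users, shifts the mean by 12–20% of the control mean and not by 33%. A shift of 33% has a probability of about 1.2% even at threefold consumption.
- **That the t-test is biased or invalid.** Under randomisation it is neither.

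**What to change.** Leave eligibility unchanged.

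1. Add to the Data section: preoperative opioid use, taken from the medication list at consent (yes/no, and daily morphine equivalents if yes).
2. In the Statistical Analysis section, prespecify an ANCOVA of 24-hour morphine equivalents with treatment and preoperative opioid use (yes/no) as terms, reporting the adjusted difference with its 95% CI. Keep the unadjusted t-test as a supporting analysis.
3. Give the existing normality and variance check a consequence: if the data are skewed by a criterion fixed in advance, fit the same model to log consumption, with the handling of zeros stated. Under the assumptions above this has higher power than the raw-scale ANCOVA. It estimates a ratio, which suits a target expressed as a percentage reduction.

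Surgical service is a natural further candidate, but its value was not examined here and it is not part of this recommendation.

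The cost is one chart item for each of 72 patients, one model statement, and one residual degree of freedom (72 − 3 = 69 instead of 72 − 2 = 70). Sample size and patient care are unaffected. The model must be written down before outcomes are seen, so that the choice of covariate cannot depend on the result.

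### Fisher's exact test for PONV and anxiety has a true type I error of at most 2.8% at 36 per group, and so gives up power that Boschloo's exact test keeps

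*Combined protocol and SAP*

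**What the plan says.** The Statistical Analysis section of the combined protocol and SAP assigns tests by type of variable. Continuous variables go to an unpaired t-test ("two-sample assuming equal variances, two-tail significance p<0.05, 95% confidence interval"). Proportions go to a "non-parametric Fisher's Exact Chi-square test, when applied to 2x2 tables", with significance declared at p ≤ 0.05. No other test for a proportion is named.

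The Data section lists "incidence of PONV" and the incidence of postoperative anxiety among the outcomes by which efficacy is judged, each recorded at 1 and 24 hours. The Hypothesis and Outcomes section makes PONV and anxiety two of four hypothesised effects, beside opioid requirement and pain. Expected rates, target differences and power are not given for either.

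The sample size statement is a separate matter. It is described as "A binary outcome, superiority power analysis based on a rate of 33% reduction of opioid consumption" and it "concluded 72 participants (36 patients per group) would be necessary to achieve 80% power with a p<0.05".

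**The concern.** Fisher's test fixes both margins of the 2x2 table, so its p-value can take only a few values. In a small trial the largest attainable p-value at or below 0.05 is often well below 0.05. The test is then stricter than its nominal level, and the unused error probability is paid for in power.

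With 36 patients per group this could matter. PONV and anxiety have no other between-group test in the plan, and the trial was not sized for them. A real reduction could fail to reach significance because of the test chosen, when another exact test with the same 5% guarantee would have detected it.

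**Working it through.** **Inputs.** From the Statistical Analysis section: 36 per group, equal allocation, significance at 0.05, Fisher's test. Assumed: two-sided testing (the plan says two-tail only for the t-test), no dropout, and all event rates, since the documents give none.

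**1. The plan's own figure.** The usual formula for two proportions is

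n = [1.960·√(2p̄(1−p̄)) + 0.842·√(p₁(1−p₁) + p₂(1−p₂))]² / (p₁−p₂)², where p̄ is the mean of p₁ and p₂.

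- 66% v 33%: p̄ = 0.495, and (1.960 × 0.7071 + 0.842 × 0.6675)² / 0.33² = 34.8, so 35 per group.
- 88% v 59% (a relative 33% cut): 36 per group.
- 47.5% v 14.5%: 29.6 without correction. With the continuity correction, (29.6/4) × [1 + √(1 + 4/(29.6 × 0.33))]² = 35.4, so 36 per group.

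The figure of 36 can therefore be reached by several routes. The plan gives no control rate, does not say whether 33% is absolute or relative, and does not name the formula.

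**2. True size.** For every pair (x, y) with x and y from 0 to 36 (37 × 37 = 1,369 tables), compute the two-sided p-value and mark the table if p ≤ 0.05. For a common rate π, the size is the sum over marked tables of Bin(x; 36, π) × Bin(y; 36, π). Then maximise over π.

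- Fisher: maximum 2.79%, at π of about 0.32.
- Boschloo: maximum 4.9%. It uses Fisher's p-value as the test statistic and takes its own p-value as the largest probability, over π, of a result at least as extreme.
- Uncorrected chi-square: maximum 5.8%, so it does not hold the 5% level.

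Boschloo rejected every table that Fisher rejected, without exception. This step needs no assumed event rate.

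**3. Power at illustrative rates.** Same enumeration, with p₁ and p₂ in place of π. The gain is taken from the unrounded powers.

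| Control v treated | Fisher | Boschloo | Gain (points) |
|---|---|---|---|
| 30% v 10% | 47% | 58% | 10 |
| 25% v 5% | 57% | 69% | 12 |
| 40% v 15% | 58% | 68% | 9 |
| 50% v 25% | 50% | 59% | 9 |

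The gain is not constant. At 47.5% v 14.5% it is 5.6 points, and at more extreme rates it is smaller.

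**4. One table.** For 3/36 v 10/36 the margins fix 13 events among 72 patients. Fisher's two-sided p is twice the hypergeometric probability of 3 or fewer in the first group, which is 0.063. Boschloo's p is 0.044. The same data are significant at 0.05 under one exact test and not under the other.

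**The case against.** The strongest defence is that Fisher's test is valid, familiar and pre-specified. Its conservatism is a known trade-off and contradicts nothing in the plan, and preferring an unconditional test is partly a matter of taste. This stands in part: nothing here is an error, and the type I error is protected. But the trade brings the trial nothing, because Boschloo protects the same 5%, rejects whenever Fisher does, and has more power at every pair of rates tabulated.

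A second objection is that the power figures depend on chosen rates. That is true of power and is why several pairs are shown. It does not touch the 2.8% ceiling, which holds for any common rate.

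A reader might go further and infer that the trial misses its stated 80% power because Fisher's test is used. The documents do not support that, for two reasons.

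- The 80% belongs to a calculation "based on a rate of 33% reduction of opioid consumption in the auricular battlefield acupuncture group compared to controls". The Data section records opioid use in morphine equivalents, and the Statistical Analysis section sends continuous variables to the t-test. No dichotomy of opioid use is defined, so as written Fisher's test is never applied to that outcome. PONV and anxiety have no stated power to miss.
- Even if opioid use were dichotomised, the answer would turn on a control rate that is not given. Fisher's power at 36 per group is 72.8% at 66% v 33%, but 82.3% at 47.5% v 14.5%, and both pairs lead to about 36 under a standard formula.

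A reader might also infer from the phrase Fisher's Exact Chi-square that the choice between two tests has been left open. The two do disagree: in 34 tables (counts x < y) the uncorrected chi-square reaches p ≤ 0.05 and Fisher does not. But the phrase leads with Fisher's exact test, and the natural reading is Fisher. The point is one of wording, and naming a single test removes it.

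**Conclusion.** The point holds as an avoidable loss of power for PONV and anxiety. At 36 per group, two-sided Fisher at 0.05 has a true type I error of at most 2.8%, against at most 4.9% for Boschloo. Over the four illustrative pairs the power given up is about 9 to 12 points.

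The size result rests only on 36 evaluable patients per group and two-sided testing at 0.05. The power losses rest also on assumed event rates, and they are not bounds for every rate. The point carries no conclusion about the sample size or the 80% figure, and it offers no restated power for the opioid outcome. It affects how readily true differences are found and does not call into question any significant result that Fisher's test would give.

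**What to change.** In the Statistical Analysis section, replace the Fisher wording for PONV and anxiety with a sentence such as: The proportions of patients with PONV and with anxiety at each assessment will be compared between groups by Boschloo's unconditional exact test, two-sided, at the 0.05 level, and the risk difference will be reported with a 95% score confidence interval. If other 2x2 comparisons, such as needle-site events, stay with Fisher's exact test, name it without the words chi-square.

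Make the change before outcomes are examined by group, so that the choice of test cannot follow the data. It needs one sentence and no further patients or measurements, and the test is available in standard software. The only downside is a less familiar test.

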# **HYPOTHESIS AND OUTCOMES:**

The study hypothesis is that perioperative battlefield acupuncture for general surgery and urology cases undergoing general anesthesia will decrease opioid requirements, postoperative pain, the incidence of PONV, and the incidence of perioperative anxiety in comparison to simulated (placebo) perioperative battlefield acupuncture.

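### No primary outcome, primary time point or success rule is named, and the one outcome that sets the sample size is powered in a form the plan does not analyse

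*Combined protocol and SAP*

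**What the plan says.** Four places bear on what the trial is meant to show.

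- **Hypothesis and Outcomes** states that acupuncture "will decrease opioid requirements, postoperative pain, the incidence of PONV, and the incidence of perioperative anxiety". The four effects are not ranked, and no rule says how many must be shown.
- **Data** gives a different list for efficacy: "Assessment of the battlefield acupuncture efficacy will be performed by testing the incidence of PONV, incidence of postoperative anxiety, and pain". Opioid use is not in that sentence.
- **Data** then sets the recording schedule, "At times 1 hour and 24 hours the following will be assessed". The items are PONV, anxiety, pain at rest and with activity, "Postoperative opioid consumption via morphine equivalents used" and "Patient satisfaction with analgesia score". Neither time is given priority.
- **Statistical Analysis** compares the two "study groups on all continuously scaled variables" by t-test and compares proportions by Fisher's exact test. The general rule is "Statistical significance will be set at a p-value" of at most 0.05, with no adjustment, ordering or split of that level. The sample size comes from "A binary outcome, superiority power analysis based on a rate of 33% reduction of opioid consumption", giving 36 per group for 80% power.

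The words primary and secondary are not applied to any outcome or time point in the protocol text available.

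**The concern.** A confirmatory claim needs a stated target: which variable, at what time, by which test. Here the sections point to different targets. The sample-size paragraph points to opioid use, the efficacy sentence in Data points to PONV, anxiety and pain, and the hypothesis names all four.

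Following the plan as written, several group comparisons could be put forward as the efficacy result once the data are seen, and a reader could not tell whether the one chosen was the one intended.

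The power statement is affected as well. It treats opioid use as a yes/no event that is never defined, while the variable recorded is an amount that the plan would analyse by t-test. The 80% therefore belongs to a test the plan does not describe.

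**Working it through.** **Inputs.** From Statistical Analysis: two-sided 0.05 for each t-test, 0.05 as the general level, 36 per arm, 80% power, a 33% reduction. From Data: six measures and two times. Assumed, because the documents give no value: control event rate or coefficient of variation for opioid use, event rates of 10–50% for PONV and anxiety, and the correlation between outcomes.

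**1. The plan's own figure.** For two proportions,

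n per arm = [1.960√(2p̄(1−p̄)) + 0.842√(p₁(1−p₁)+p₂(1−p₂))]² / (p₁−p₂)².

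Reading 33% as an absolute difference, at 66.5% v 33.5%: (1.386 + 0.562)² / 0.1089 = 34.8, so 35 per arm, close to the stated 36. Reading it as a relative reduction gives 33 per arm at a 90% control rate, 49 at 80%, 71 at 70% and 140 at 50%. The stated 36 is attainable, but the plan's inputs do not determine it. In each case it rests on one test at 0.05.

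**2. The same 33% for the variable recorded.** For a difference in means, n = 2(1.960+0.842)² CV² / 0.33². At an assumed CV of 0.5 this is 3.925/0.1089 = 36.04, so 37 per arm. By the normal approximation, power at 36 per arm is 94% at CV 0.4, 80% at 0.5, 52% at 0.7 and 29% at 1.0. It may be adequate or poor; the documents do not allow a choice.

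**3. Number of group comparisons.** This count is mine; safety items and the analysis over time are excluded.

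| Reading | t-tests | Fisher tests | Total |
|---|---|---|---|
| Six measures, both times | 8 | 4 | 12 |
| Without satisfaction, both times | 6 | 4 | 10 |
| Efficacy sentence in Data, both times | 4 | 4 | 8 |
| Six measures, once each | 4 | 2 | 6 |
| Without satisfaction, once each | 3 | 2 | 5 |
| Efficacy sentence in Data, once each | 2 | 2 | 4 |

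**4. Actual size of Fisher's test**, 36 v 36, by enumeration at event rates of 10, 20, 30, 40 and 50%: 1.38, 2.58, 2.77, 2.57 and 2.47%. These sizes (s), not a nominal 5%, are used below.

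**5. Chance of at least one significant result with no treatment effect, independent tests.**

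- Either direction: 1 − 0.95^t (1−s)^f. For 12 tests: 1 − 0.6634×0.9459 = 0.372 to 1 − 0.6634×0.8937 = 0.407.
- Favouring acupuncture only: 1 − 0.975^t (1−s/2)^f. For 12 tests: 1 − 0.8167×0.9727 = 0.206 to 1 − 0.8167×0.9457 = 0.228.

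| Tests | Either direction | Favouring acupuncture |
|---|---|---|
| 12 | 37–41% | 21–23% |
| 10 | 30–34% | 16–19% |
| 8 | 23–27% | 12–15% |
| 6 | 21–23% | 11–12% |
| 5 | 17–19% | 9–10% |
| 4 | 12–15% | 6–8% |

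A single t-test gives 5% and 2.5%.

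**6. Correlated outcomes**, by patient-level simulation (20,000 trials per setting, one common correlation, event rates 10, 30 and 50%).

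| Tests | Correlation | Either direction | Favouring acupuncture |
|---|---|---|---|
| 12 | 0.7 | 21–24% | 11–12% |
| 12 | 0.9 | 14–16% | 7–8% |
| 5 | 0.7 | 13–14% | 6–7% |
| 5 | 0.9 | 10–11% | about 5% |

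**7. Other success rules.** Opioid use alone, one t-test: 5% two-sided, no inflation. All four effects required, each tested once: the chance that all are significant cannot exceed the size of any test whose effect is truly absent. That is at most 1.4–2.8% if PONV or anxiety is unaffected, and at most 5% if only opioid use or pain is unaffected. Again there is no inflation.

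**The case against.** The best defence is that opioid consumption is plainly the primary outcome: it comes first in the hypothesis and is the only outcome used to size the trial. On that reading, with one test, the error rate is 5% and nothing needs adjusting. This has force, and opioid use is rightly called the implied primary. It does not settle the matter. The efficacy sentence in Data leaves opioid use out, the power paragraph gives it no event and no time, and its recorded form differs from its powered form. A reader who accepts opioid use as primary still cannot tell which variable, test or time decides the trial.

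A second defence is that the hypothesis joins its four effects with a conjunction, so all must be shown. That would not inflate error, but no such rule is written.

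Three stronger readings are tempting and are not supported.

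- **That the trial's false-efficacy rate is about 40%.** That figure needs 12 independent tests, a rule that any one result suffices, and results favouring sham counted as success. The plan states no such rule, its hypothesis is directional, and its outcomes are probably correlated.
- **That every interpretation exceeds 5%.** The opioid-only and all-four rules do not.
- **That 72 patients are too few.** The documents give neither a control rate nor a standard deviation, so this cannot be shown.

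**Conclusion.** The concern holds. The plan ranks no outcome or time point, states no success or multiplicity rule, and applies an unadjusted 0.05 throughout. The false-positive rate of an efficacy claim is therefore undefined, rather than shown to be high.

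Its size depends on a rule the plan does not give. If any one result favouring acupuncture sufficed, the rate would run from about 5% (5 tests, correlation 0.9) to 21–23% (12 independent tests), against 2.5% for a single t-test. The corresponding range for results in either direction is 10–11% to 37–41%, against 5%. These figures rest on 36 per arm, no treatment effect, assumed event rates of 10–50%, assumed correlations and my count of tests.

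Separately, and without any of those assumptions, the 80% power statement does not match the opioid variable as recorded and analysed. The plan should be corrected on both points.

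**What to change.** - Name one primary outcome at one time point, tested once at two-sided 0.05. The choice is the sponsor's. Opioid consumption in morphine equivalents over a stated period is closest to the sample-size paragraph.
- Make this choice before unblinding. The sentence on the t-test is in the past tense, so it is unclear whether data have been examined; if they have, disclose the choice as post hoc.
- Bring Hypothesis and Outcomes, Data and Statistical Analysis into line with it, including the sentence on how efficacy is assessed.
- State whether the primary outcome is binary or continuous. If binary, define the event and the control rate, and say whether 33% is absolute or relative. If continuous, give the assumed mean and standard deviation. Then restate the power at 72 patients for that form and the test to be used.
- Label all other outcomes secondary and report them as estimates with 95% confidence intervals, without stand-alone efficacy claims.

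The cost is revised wording and one power calculation, with no new measurements. The secondary outcomes lose stand-alone claims, and the restated power may be less favourable than 80%. If so, the sponsor would have to accept it openly or revisit the sample size.
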